#### 8.2. Classification of Adverse Events

#### 8.2.1. Assigning Severity Rating for Adverse Events

#### 8.2.1.1. Criteria for Determining Averse Event Severity

The Investigator will make an assessment of the severity of each AE and SAE according to the National Cancer Institute Common Terminology Criteria for Adverse Events (CTCAE), v. 5.0, 2017. For terms not specified with the CTCAE, the criteria in Table 4 should be used to determine the grade severity.

Table 4: Criteria for Determining the Grade/Severity of Adverse Event Terms Not Specified by the National Cancer Institute CTCAE

Grade	Criteria	
1	Mild; asymptomatic or mild symptoms, clinical or diagnostic observations only; intervention not indicated	
2	Moderate; minimal, local, or noninvasive intervention indicated; limiting age-appropriate instrumental activities of daily living a	
3	Severe or medically significant but not immediately life-threatening; hospitalization or prolongation of hospitalization indicated; disabling; limiting self-care activities of daily living b	
4	Life threatening consequences; urgent intervention indicated	
5	Death related to adverse event	

CTCAE = Common Terminology Criteria for Adverse Events.

- a Instrumental activities of daily living refer to preparing meals, shopping for groceries or clothes, using the telephone, managing money, etc.
- b Self-care activities of daily living refer to bathing, dressing and undressing, feeding self, using the toilet, taking medications, and not bedridden.

Adverse event severity should be recorded in the appropriate section of the adverse event case report form and in the subject's source documents.

#### 8.2.1.2. Toxicity Management Criteria

#### 8.2.1.2.1. Grade 1 or Grade 2 Adverse Event

Subjects who develop a Grade 1 or Grade 2 AE may continue investigational product at the discretion of the Investigator. Subjects who choose to withdraw from study due to a Grade 1 or 2 AE should have study withdrawal/follow-up evaluations completed.

#### 8.2.1.2.2. Grade 3 Adverse Event

Subjects who develop a Grade 3 AE should be managed as follows:

- If the Investigator has compelling evidence that the Grade 3 AE has not been caused by investigational product, then dosing may continue after discussion with the Medical Monitor.
- Subjects who develop a Grade 3 AE that the Investigator considers related or possibly related to investigational product should have the investigational product discontinued. Subjects experiencing Grade 3 AEs requiring permanent discontinuation of investigational product should be followed weekly until resolution or stability of the AE and encouraged to have withdrawal study evaluations completed.

#### 8.2.1.2.3. Grade 4 Adverse Event

Subjects who develop a Grade 4 AE should have investigational product permanently discontinued.

Subjects experiencing Grade 4 AEs requiring permanent discontinuation of investigational product should be followed weekly until resolution or stability of the AE and encouraged to have withdrawal study evaluations completed.

#### 8.2.1.2.4. Other Management Criteria:

The Medical Monitor should be notified if any of the following occur:

• Severe signs or symptoms, or significant changes in any of the safety assessments, that put the safety of the subject at risk (eg, laboratory tests or vital signs, etc.) as judged by the Investigator.

#### 8.2.2. Assigning Causal Relationship to Study Drug

The Principal Investigator is to make the causality assessment. Causality assessment is not to be delegated; however, if delegation is unavoidable due to investigator inaccessibility, this must be recorded as a protocol deviation. The reasonable possibility of the relationship of an adverse event to study drug is to be assessed with careful medical consideration at the time of evaluation of an adverse event. The following definitions are to be used for the relationship of the adverse event to study drug:

- Related: A clinical event, including laboratory test abnormality, with a temporal relationship to study drug administration that makes a causal relationship plausible, unlikely attributed to concurrent disease or other drugs or chemicals, and that follows a clinically reasonable response on re-administration (rechallenge) or withdrawal (dechallenge), although information on drug withdrawal may be lacking or unclear.
- **Not related**: A clinical event, including laboratory test abnormality, with a temporal relationship to study drug administration that makes a causal relationship improbable and/or in which other drugs, chemicals, or underlying disease provide a plausible explanation.

Any AEs /SAEs assessed as related to study participation (eg, protocol-mandated procedures, invasive tests, or change in existing therapy) or related to study drug will be recorded from the time a subject consented to participate in the study up to and including any follow-up contact.

All AEs, whether related to study drug or not, must be fully and completely documented on the AE page of the eCRF and in the subject's clinical record. In the event a subject is withdrawn from the study because of an AE, the primary reason for withdrawal (ie, due to an AE) must be recorded on the eCRF as such.

## 8.3. Time Period and Frequency for Event Assessment and Follow-Up

#### **8.3.1.** Adverse Event Reporting

All AEs will be collected from the time of signed informed consent until the final visit.

Any AEs assessed as related to study participation (eg, protocol-mandated procedures, invasive tests, or change in existing therapy) will be collected from the time a subject consented to participate in the study up to and including any follow-up contact.

All SAEs will be recorded in the eCRF and reported to the Sponsor within 24 hours via email or phone (refer to Medical Monitor/Sponsor Information page for contact information) (see Section 8.4).

#### **8.3.2.** Follow-Up of Adverse Events

After the initial AE/SAE report, the Investigator is required to proactively follow each subject at subsequent visits/contacts. All SAEs and nonserious AEs will be followed until resolution, until the condition stabilizes, until the event is otherwise explained, or until the subject is lost to follow-up.

The Investigator will assess the outcome of each AE using the following criteria:

- **Recovered/Resolved:** The event has improved or subject recuperated.
- Recovered/Resolved with sequelae: The subject has recuperated but retained pathological conditions resulting from the prior disease or injury.
- **Recovering/Resolving**: The event is improving.
- Not recovered/Not resolved: The event has not improved or subject recuperated.
- **Unknown**: The outcome of the event is not known, not observed, not recorded, or refused.
- **Fatal:** Termination of life as an outcome of the AE.

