#### 12.9.1 Adverse Events

AE terms will be coded using the MedDRA dictionary. A treatment-emergent AE (TEAE) is defined as an AE that starts after the first dose of study medication. For subjects not rolling over to Open-label study, all reported AEs will be included in the Double-Blind phase summaries. For subjects rolling over to the Open-label study, all AEs with an onset date on or before the Week 12 visit date will be included in the Double-Blind phase summaries.

If relationship to treatment is missing, the event will be conservatively treated as related to study drug. Missing severity will be imputed to the highest severity level (most severe).

All AEs will be listed by treatment and by subject, detailing the verbatim term given by the investigator, the preferred term (PT), system organ class (SOC), onset date and time, end date and time, duration (days), CTCAE grade, outcome, relationship to study drug/treatment, action taken with study drug/treatment, other action taken to treat the event, seriousness and criteria for seriousness. Serious AEs (SAEs), TEAEs leading to study discontinuation, TEAEs related to study drug will also be listed separately. The following adverse event of special interest (AESIs) will be identified and listed separately: contact dermatitis, folliculitis, and headache.

AEs will be summarized by treatment and overall as incidence rates of:

- Any AE
- Any TEAE
- Any AESIs
- Any treatment-related TEAE, including definitely, probably, and possibly related
- Any TEAE leading to study drug discontinuation
- Any SAE (non-Fatal)
- Any serious TEAE
- Death
- Treatment-related Serious TEAE
- Serious TEAE leading to study drug discontinuation

Individual PTs will be summarized by treatment according to the following:

- All TEAEs by SOC in alphabetical order and PT in descending order of combined frequency (also for treatment-related TEAEs, TEAEs leading to study discontinuation and serious TEAEs)
- All TEAEs by SOC, PT, and maximum CTCAE grade
- All TEAEs by SOC, PT, and maximum causality (not related, related) to the study drug

In addition, TEAEs and serious TEAEs will be summarized by SOC (alphabetical order) and PT (descending order) for the following subgroups:

- Age (<65 and >=65 years old)
- Sex
- Race (White, Other)

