At each level of summarization, a subject will be counted once if he/she reported one or more events. The severity of TEAEs and relationship to study drug will be summarized in a similar manner. For summaries of relationship to study drug, a subject will be classified according to the closest relationship. For summaries of TEAE CTCAE grade, a subject will be classified according to the worst grade.

For AESIs, summarization will be more extensive, reflecting the more detailed information collected. Information summarized will include number of events per subject, earliest onset day, duration (in days), causality, grade and seriousness of AESIs, outcome, actions taken with study drug, assorted physical characteristics of the AESIs, and demographic/baseline characteristics and PGA status of the subjects experiencing them. Each type of AESI will be summarized separately. If a subject has more than one treatment-emergent occurrence of an AESI, the subject's maximum duration, highest levels of causality and seriousness, maximum grade and generally the most extreme level of each characteristic will be summarized. If an AESI was ongoing at EOS, it will not be included in the duration summary.

A Kaplan-Meier figure will be generated for each AESI of time to first event. Subjects not experiencing the AESI will be censored at the date of study completion or discontinuation.

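### The adverse event outcome Recovered/Resolved is met by an event that has only improved, so an event still present can be reported as resolved

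*Protocol*

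**What the plan says.** Protocol 8.3.2 makes the outcome coding rule directive: "The Investigator will assess the outcome of each AE using the following criteria". Six categories follow, and three of them matter here:

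- Recovered/Resolved: "The event has improved or subject recuperated".
- Recovering/Resolving: "The event is improving".
- Not recovered/Not resolved: "The event has not improved or subject recuperated".

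The other three cover recovery with sequelae, unknown outcome and death.

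The SAP uses the outcome as coded. In section 12.9.1 the listing of all AEs includes "end date and time, duration (days), CTCAE grade, outcome, relationship to study drug/treatment". For the AEs of special interest (AESIs), the same section plans a fuller summary that includes "causality, grade and seriousness of AESIs, outcome, actions taken with study drug", and adds: "Each type of AESI will be summarized separately". The AESIs are contact dermatitis, folliculitis and headache.

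**The concern.** The three definitions separate resolved from unresolved events by whether there was improvement, not by whether the event is still there. A reader of an outcome table takes resolved to mean that the event has cleared. Under the written definition it may mean only that the event is less severe than it was.

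What is at stake is how clearly the safety outputs describe local reactions and headache. Protocol 8.1.3 singles these events out as clinically important, and Protocol 1.1.2 says the results are meant to support registration. If some sites follow the category label and others follow the definition, the same clinical course will be coded in different ways.

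**Working it through.** There is no plan figure to reproduce and no calculation to run. The check sets the definitions against the possible states of an event, looks for any text that overrides them, and traces where the outcome is used.

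**1. Definitions against states.** Take a nonfatal AE with known outcome and no sequelae. I read the Not recovered/Not resolved definition as neither improved nor recuperated.

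| State of the event | Recovered/Resolved | Recovering/Resolving | Not recovered/Not resolved |
|---|---|---|---|
| A. Gone | met | not met | not met |
| B. Present, still improving | met | met | not met |
| C. Present, improved, now stable | met | not met | not met |
| D. Present, not improved | not met | not met | met |

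Recovered/Resolved is met in 3 of 4 states (A, B, C), while the event is absent in 1 of 4 (A). So 2 of the 3 states that meet it have the event still present. State B fits two categories, and the definitions give no basis for choosing between them. In state C, following the definitions leads to the resolved code, and an investigator has to depart from them to code the event correctly. This is a count of what the wording permits. The states carry no frequencies, so it does not estimate how often miscoding would occur.

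**2. State C is one the protocol expects.** Section 8.3.2 says: "All SAEs and nonserious AEs will be followed until resolution, until the condition stabilizes, until the event is otherwise explained". Section 8.4.1 repeats this for serious AEs, and sections 8.2.1.2.2 and 8.2.1.2.3 apply a similar rule to Grade 3 and 4 events that require permanent discontinuation of study drug. Follow-up may therefore end on a stable event that has not resolved. If that event improved before it stabilised, the outcome list has no correct place for it.

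**3. Any overriding text.** Neither document has another definition of AE resolution. Protocol 6.3.4 refers to laboratory values returning to normal or baseline, but that governs repeat testing and not outcome coding. The SAP does not redefine or re-derive outcome. The amendment summary in Protocol Appendix 9 lists no change to section 8.3.2.

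**4. Where the outcome is reported.**

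- Listing of all AEs (SAP 12.9.1): affected.
- Outcome part of the three separate AESI summaries: affected. For a subject with repeat occurrences the SAP generally takes the most extreme level of each characteristic, so that subject's entry changes only if the miscoded event was the worst one.
- The 10 overall AE incidence rows in SAP 12.9.1: none uses the boundary between resolved and resolving.
- AESI duration: SAP section 9 works from start and end dates, and the exclusion of events ongoing at end of study does not refer to the outcome code. No effect is claimed.
- Ending follow-up, and restarting study drug after an AESI (Protocol 8.1.3): these rules do not refer to the outcome code. No effect is claimed.

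**The case against.** The strongest reply is that the list should be read as a whole. The labels contrast a completed process with one in progress, and Recovering/Resolving would be nearly redundant if any improvement counted as resolved. The follow-up rules treat resolution and stability as different endpoints, so the protocol evidently does not regard an improved, stable event as resolved. An investigator would have to choose a resolved label for an event known to be present when a resolving label was available. The listing prints the end date beside the outcome, so a resolved event without an end date would be visible, and Protocol section 9 says that inconsistencies are queried. Some improved events with a lasting residue might also fit the sequelae category.

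Much of this stands as evidence of intent: full resolution was almost certainly meant, and many investigators will code accordingly. It does not repair the text. The instruction is to use the written criteria, and those contradict the labels. The follow-up rules do not define outcome codes, and they show that state C is foreseen. The sequelae category requires that the subject has recuperated, and the state table sets it aside. The documents specify no check that reconciles outcome with end date. The case report form and its completion instructions are not in the documents, so actual coding practice cannot be judged either way. It also stands that the 3-of-4 count describes wording only, and that the practical consequence is small.

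**Conclusion.** The concern holds. As written, Recovered/Resolved includes events that have improved but are still present. The three categories overlap for an event that is still improving, and they give the wrong code for one that improved and then stabilised.

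Confidence is high for the wording. The number of events affected is unknown, because the documents give no AE outcome data. The effect is limited to one descriptive field, in the AE listings and in the three AESI outcome summaries. No difference between arms is implied, and the SAP makes no formal comparison of safety data. Efficacy, power and type I error are untouched. This is a minor correction worth making because it is simple. The conclusion assumes that sites apply the definitions as written and that no completion instruction outside the documents overrides them.

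**What to change.** Reword three definitions in Protocol 8.3.2:

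- **Recovered/Resolved:** the event is no longer present, or the subject has returned to the pre-event state.
- **Recovering/Resolving:** the event has improved but is still present, whether or not it is still improving.
- **Not recovered/Not resolved:** the event is present without improvement.

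States A to D then each fall in exactly one of these categories, and the definitions agree with their labels. The cost is three reworded definitions, with no added visits, data collection or analyses.

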## **8.4.** Reporting Procedures

#### 8.4.1. Serious Adverse Event Reporting

When an Investigator determines that an AE meets the protocol definition of an SAE during the study, he/she must notify the Sponsor using an SAE Report Form within 24 hours of the study site personnel's knowledge of the event, regardless of the Investigator assessment of the relationship of the event to study drug. Relevant information will be entered on the AE page and on all other applicable pages of the eCRF; source documentation should not be sent with the SAE Report Form unless requested.

Follow-up information received on SAEs should be faxed to the Sponsor within 1 business day of receipt (refer to Medical Monitor/Sponsor Information page for contact information). This information should be included on a follow-up SAE form and placed with the original SAE information.

All SAEs will be followed until resolution, until the condition stabilizes, until the event is otherwise explained, or until the subject is lost to follow-up.

The completed SAE Report form should be submitted via email or fax to the SAE Reporting Contact which can be found on the Medical Monitor/Sponsor Information Page of this protocol.

Do not delay reporting a suspected SAE in order to obtain additional information. Any additional information, if collected, can be reported as a follow-up to the initial report.

## 8.4.2. Regulatory Reporting Requirements for Serious Adverse Events

Prompt notification by the Investigator to the Sponsor of SAEs (even for non-interventional post-marketing studies) is essential so that legal obligations and ethical responsibilities towards the safety of subjects and the safety of a product under clinical investigation are met.

The Sponsor has a legal responsibility to notify both the local regulatory authority and other regulatory agencies about the safety of a product under clinical investigation. The Sponsor will

comply with country-specific regulatory requirements relating to safety reporting to the regulatory authority, IRB/IEC, and Investigators.

Investigator safety reports are prepared for suspected unexpected serious adverse reactions according to local regulatory requirements and are forwarded to Investigators as necessary.

An Investigator who receives an Investigator safety report describing a SAE(s) or other specific safety information (eg, summary or listing of SAEs) from the Sponsor will file it with the Investigator's Brochure and will notify the IRB/IEC, if appropriate, according to local requirements.

## 8.5. Pregnancy Management and Reporting

Any female subject who becomes pregnant during the study will be withdrawn. Details will be collected for all pregnancies in female subjects and female partners of male subjects that begin after the start of dosing and through the Follow-up visit. Pregnancy is not automatically considered an AE.

If a pregnancy is reported, then the Investigator should complete a Pregnancy Report Form and submit via email or fax to the Pregnancy Reporting Contact for which contact information can be found on the Medical Monitor/Sponsor Information Page of this protocol, within 2 weeks of learning of the pregnancy. The subject will also be followed to determine the outcome of the pregnancy. Information on the status of the mother and child will be forwarded to the Sponsor. Generally, follow-up will be no longer than 6 to 8 weeks following the estimated delivery date. Any premature termination of the pregnancy will be reported.

Any SAE occurring in association with a pregnancy brought to the Investigator's attention after the subject has completed the study and considered by the Investigator as possibly related to the study drug must be promptly reported to the Sponsor or the Sponsor's representative.

The Investigator must attempt to collect pregnancy information on any female partners of male study subjects who become pregnant while the subject is enrolled in the study. Pregnancy information must be reported to the Sponsor or the Sponsor's representative as described above. The partner will also be followed to determine the outcome of the pregnancy. Information on the status of the mother and child will be forwarded to Sponsor or the Sponsor's representative. Generally, follow-up will be no longer than 6 to 8 weeks following the estimated delivery date. Any premature termination of the pregnancy will be reported on the pregnancy report form.

## 8.6. Safety Oversight

No independent Data Monitoring Committee will be used for this study; however, the Sponsor (including the Medical Monitor) will monitor safety on a periodic basis throughout the study.

#### 9. DATA MANAGEMENT

For this study, subject data will be entered into the Sponsor-defined eCRFs, transmitted electronically to the Sponsor or designee, and combined with data provided from other sources in a validated data system.

Management of clinical data will be performed in accordance with applicable Sponsor standards and data cleaning procedures will be used to ensure the integrity of the data, eg, errors will be corrected, and inconsistencies queried in the data.

Adverse events and relevant medical history will be coded using the most current version of the Medical Dictionary for Regulatory Activities (MedDRA). Concomitant medications will be coded with the most current version of World Health Organization Drug Global Dictionary (WHODrug Global).

The Investigator will retain original source documents and the Sponsor will receive CRF-required data as electronic datasets. Subject initials will not be collected or transmitted to the Sponsor.

#### 10. STATISTICAL CONSIDERATIONS AND DATA ANALYSES

This study will evaluate the efficacy and safety of tapinar of cream, 1% compared with vehicle control cream in adults with plaque psoriasis.

